#### **7.1.2.6.5 RECIST 1.1 Assessment of Disease**

RECIST 1.1 will be used by BICR as the primary measure for assessment of tumor response, date of disease progression, and as a basis for all protocol guidelines related to disease status (e.g., discontinuation of study treatment). Although RECIST 1.1 references a maximum of 5 target lesions in total and 2 per organ, the Sponsor allows a maximum of 10 target lesions in total and 5 per organ, if clinically relevant to enable a broader sampling of tumor burden.

#### **7.1.2.6.6 iRECIST Assessment of Disease**

iRECIST is based on RECIST 1.1, but adapted to account for the unique tumor response seen with immunotherapeutic drugs. iRECIST will be used by the investigator to assess tumor response and progression, and make treatment decisions. When clinically stable, subjects should not be discontinued until progression is confirmed by the investigator, working with local radiology, according to the rules outlined in Section 12.4. This allowance to continue treatment despite initial radiologic PD takes into account the observation that some subjects can have a transient tumor flare in the first few months after the start of immunotherapy, and then experience subsequent disease response. This data will be captured in the clinical database.

Clinical stability is defined as the following:

- Absence of symptoms and signs indicating clinically significant progression of disease
- No decline in ECOG Performance Status
- No requirements for intensified management, including increased analgesia, radiation, or other palliative care

Any subject deemed **clinically unstable** should be discontinued from study treatment at site-assessed first radiologic evidence of PD, and is not required to have repeat tumor imaging for confirmation of PD by iRECIST.

If the investigator decides to continue treatment, the subject may continue to receive study treatment and the tumor assessment should be repeated 4 to 8 weeks later to confirm PD by iRECIST, per investigator assessment. Images should continue to be sent in to the central imaging vendor for potential retrospective BICR.

If repeat imaging does not confirm PD per iRECIST, as assessed by the investigator, and the subject continues to be clinically stable, study treatment may continue and follow the regular imaging schedule. If PD is confirmed, subjects will be discontinued from study treatment.

If a subject has confirmed radiographic progression (iCPD) as defined in Section 12.4, study treatment should be discontinued; however, if the subject is achieving a clinically meaningful benefit, an exception to continue study treatment may be considered following consultation with the Sponsor. In this case, if study treatment is continued, tumor imaging should continue to be performed following the intervals as outlined in the Trial Flow Chart in Section 6 and submitted to the central imaging vendor.

A description of the adaptations and iRECIST process is provided in Section 12.4, with additional details in the iRECIST publication [1]. A summary of imaging and treatment requirements after first radiologic evidence of progression is provided in [Table 8](#) and illustrated as a flowchart in [Figure 3](#).

[figure not shown]
Table 8 Imaging and Treatment After First Radiologic Evidence of Progressive Disease

	Clinically Stable		Clinically Unstable	
	Imaging	Treatment	Imaging	Treatment
First radiologic evidence of PD by RECIST 1.1 per investigator assessment.	Submit the imaging to BICR for verification. Repeat imaging at 4 to 8 weeks to confirm PD per iRECIST.	May continue study treatment at the discretion of the investigator.	Submit the imaging to BICR for verification.	Discontinue study treatment
Repeat tumor imaging confirms PD (iCPD) by iRECIST per investigator assessment	No additional imaging required.	Discontinue study treatment (exception is possible upon consultation with Sponsor).	No additional imaging required.	Not applicable
Repeat tumor imaging shows iUPD by iRECIST per investigator assessment	Repeat imaging at 4 to 8 weeks to confirm PD.	Continue study treatment at the investigator's discretion.	No additional imaging required.	Discontinue study treatment
Repeat tumor imaging shows iSD, iPR, or iCR by iRECIST per investigator assessment.	Continue regularly scheduled imaging assessments.	Continue study treatment at the investigator's discretion.	No additional imaging required.	Discontinue study treatment

Abbreviations: BICR=blinded independent central review; iCPD=iRECIST confirmed progressive disease; iCR=iRECIST complete response; iRECIST=modified Response Evaluation Criteria in Solid Tumors 1.1 for immune-based therapeutics; iPR=iRECIST partial response; iSD=iRECIST stable disease; iUPD=iRECIST unconfirmed progressive disease; PD=progressive disease; RECIST 1.1=Response Evaluation Criteria in Solid Tumors 1.1.

Note: If progression has been centrally verified, further management is by the site, based on iRECIST. Any further imaging should still be submitted to the central imaging vendor, but no rapid review will occur. If RECIST 1.1 PD has not been centrally verified, ideally the site should continue treatment. Whether or not treatment continues, imaging should be collected and submitted to the central imaging vendor with verification of progression (VOP) request until RECIST 1.1 PD is verified by BICR.

Figure 3 Imaging and Treatment for Clinically Stable Subjects After First Radiologic Evidence of PD Assessed by the Investigator

### 7.1.2.7 Tumor Tissue Collection

Programmed death-ligand 1 expression will be tested by a central laboratory as part of screening. Only subjects whose tumors demonstrate PD-L1 expression (TPS  $\geq 50\%$ ) are eligible for enrollment.

Archival tumor tissue sample or newly obtained core or excisional biopsy of a tumor lesion not previously irradiated must be provided to the central laboratory for testing. Formalin-fixed, paraffin-embedded tissue blocks are preferred to slides. Newly obtained biopsies are preferred to archived tissue.

If the subject signs the FBR consent, any leftover tissue biopsies that would ordinarily be discarded at the end of the main study will be retained for FBR, again providing the subject has signed the FBR consent.

Detailed instructions for tissue collection, processing and shipment are provided in the Procedures Manual. Older biopsy material or surgical specimens may be used to assess *EGFR* mutation.

### 7.1.2.8 Patient-reported Outcomes

**NOTE: As of Amendment 06, PROs will no longer be collected. This section is no longer applicable and has been deleted.**

### 7.1.3 Laboratory Procedures/Assessments

Details regarding specific laboratory procedures/assessments to be performed in this trial are provided below. The total amount of blood/tissue to be drawn/collected over the course of the trial (from pre-trial to post-trial visits), including approximate blood/tissue volumes drawn/collected by visit and by sample type per subject can be found in the Trial Procedures Manual. Refer to Section 6 – Trial Flow Chart for the timing of laboratory assessments.

#### 7.1.3.1 Laboratory Safety Evaluations (Hematology, Chemistry and Urinalysis)

**NOTE: As of Amendment 06, ipilimumab and matching placebo have been removed from the study. This section has been updated accordingly.**

Laboratory tests for hematology, chemistry and urinalysis are specified in [Table 9](#). These tests are required at visits as noted in the Trial Flow Charts (Section 6) or as clinically indicated.

Table 9 Laboratory Tests

Hematology	Chemistry	Urinalysis	Other
Hematocrit	Albumin	Blood	FSH
Hemoglobin	Alkaline phosphatase	Glucose	Serum $\beta$ -hCG
Platelet count	ALT	Protein	Triiodothyronine (FT3 or T3)
WBC (total and/or differential) RBC	AST	Specific gravity	Thyroxine (FT4 or T4)
	Carbon dioxide (CO 2 or bicarbonate) a	Microscopic examination, if abnormal results are noted	TSH
	Calcium		ACTH level c
	Chloride		PT (INR)
	Creatinine		aPTT/PTT
	Glucose		
	Magnesium		
	Phosphorus		Blood for FBR (optional)
	Potassium		Blood for genetics
	Sodium		Blood for correlative studies
	Total bilirubin		Blood for biomarkers
	Direct bilirubin, if total bilirubin is elevated above the ULN		

Hematology	Chemistry	Urinalysis	Other
	Total protein		
	BUN b		
	Urea b		
	Uric acid		

a If these tests are not done as part of standard of care in your region, then these tests do not need to be performed.

b BUN or urea should be collected per institutional standard. It is not required to perform both of these laboratory tests.

c Perform ACTH testing as clinically indicated.

Abbreviations: ACTH = adrenocorticotropic hormone; ALT = Alanine aminotransferase; AST = aspartate aminotransferase; BUN=Blood urea nitrogen; β-hCG=beta-human chorionic gonadotropin; CBC=complete blood count; CO2=Carbon dioxide; FBR = future biomedical research; FSH=Follicle stimulating hormone; PPT/INR=Prothrombin time/international normalized ratio; aPTT/PTT=Activated prothrombin time/partial thromboplastin time; TSH = thyroid stimulating hormone; WBC=white blood cell.

Laboratory tests for screening or entry into the Second Course Phase should be performed within 10 days prior to the first dose of trial treatment. After Cycle 1, predose laboratory procedures can be conducted up to 7 days prior to dosing.

All protocol-required screening and safety laboratory results must be reviewed by the investigator or qualified designee and found to be acceptable prior to each dose of trial treatment.

Note: For endocrine testing (TSH, FT3/T3, FT4/T4, and ACTH as listed above), where results are not available prior to the dose of trial treatment, testing must be reviewed by the investigator or qualified designee and found to be acceptable prior to the following dose of trial treatment (eg, within 3 weeks of the laboratory procedure date).

### 7.1.3.2 Pregnancy Test

For all women who are being considered for participation in the trial, and who are of reproductive potential, a serum pregnancy test after screening should be repeated if required by local guidelines. Subjects must be excluded/discontinued from the trial in the event of a positive or borderline-positive test result.

### 7.1.3.3 Pharmacokinetic/Pharmacodynamic/Immunogenicity Evaluations

**NOTE: As of Amendment 06, pharmacokinetic, pharmacodynamic, and immunogenicity evaluations will not be pursued and blood samples for these endpoints will not be collected. This section is no longer applicable and has been deleted.**

### 7.1.3.4 Molecular Testing

Site must be able to provide documentation of subject’s tumor *EGFR* mutation and/or *ALK* translocation status. Investigators must be able to produce the source documentation of the *EGFR* mutation and *ALK* translocation in all subjects with nonsquamous histologies AND for subjects in whom testing is clinically recommended. If either an *EGFR*-sensitizing mutation or *ALK* translocation is detected, additional information regarding the mutation status of the other molecule is not required. If documentation is unavailable or the site is unable to test for these molecular changes, formalin-fixed paraffin-embedded tumor tissue of any age should be submitted to a local laboratory designated by the Sponsor for such testing. If the site is unable to provide this source documentation, then the Sponsor will offer this molecular

testing of the tumor. Tissue PD-L1 testing is assessed by IHC as determined by an FDA-approved test (22C3 Pharm IHC PharmDx [Dako]) assay) at a central laboratory. Local testing of PD-L1 is NOT allowed per protocol. Detailed instructions for tissue collection, processing, and shipment are provided in the Procedures Manual.

If treatment with ROS1-targeted therapy and testing for *ROS1* are approved and accessible, then local testing for *ROS1* is required. Testing for ROS1 is not required in subjects whose tumor is known to have predominantly squamous histology, and in subjects where *ROS1*-targeted therapy is not accessible.

### **7.1.3.5 Planned Genetic Analysis Sample Collection**

Sample collection, storage and shipment instructions for Planned Genetic Analysis samples will be provided in the Procedure Manual. Samples should be collected for planned analysis of associations between genetic variants in germline/tumor DNA and drug response. If a documented law or regulation prohibits (or local IRB/Independent Ethics Committee [IEC] does not approve) sample collection for these purposes, then such samples should not be collected at the corresponding sites. Leftover DNA extracted from planned genetic analysis samples will be stored for future biomedical research only if subject signs the Future Biomedical Research consent.

### **7.1.3.6 Future Biomedical Research Samples**

The following specimens are to be obtained as part of Future Biomedical Research:

- DNA for future research
- Leftover main study tumor tissue
- Leftover RNA from RNA analyses
- Leftover plasma from plasma biomarker analyses
- Leftover serum from serum biomarker analyses

### **7.1.3.7 Medical Resource Utilization and Health Economics**

All-cause hospitalizations and emergency room visits must be reported in the eCRF, from the time of treatment allocation/randomization through 90 days following cessation of study treatment, or 30 days following cessation of study treatment if the participant initiates new anticancer therapy (whichever is earlier).

## **7.1.4 Other Procedures**

### **7.1.4.1 Withdrawal/Discontinuation**

When a subject withdraws from participation in the trial, all applicable activities scheduled for the final trial visit should be performed at the time of withdrawal. Any adverse events which are present at the time of withdrawal should be followed in accordance with the safety requirements outlined in Section 7.2 - Assessing and Recording Adverse Events.

#### 7.1.4.1.1 Withdrawal From Future Biomedical Research

Subjects may withdraw their consent for Future Biomedical Research. Subjects may withdraw consent at any time by contacting the principal investigator for the main trial. If medical records for the main trial are still available, the investigator will contact the Sponsor using the designated mailbox ([contact]). Subsequently, the subject's consent for Future Biomedical Research will be withdrawn. A letter will be sent from the Sponsor to the investigator confirming the withdrawal. It is the responsibility of the investigator to inform the subject of completion of withdrawal. Any analyses in progress at the time of request for withdrawal or already performed prior to the request being received by the Sponsor will continue to be used as part of the overall research trial data and results. No new analyses would be generated after the request is received.

In the event that the medical records for the main trial are no longer available (e.g., if the investigator is no longer required by regulatory authorities to retain the main trial records) or the specimens have been completely anonymized, there will no longer be a link between the subject's personal information and their specimens. In this situation, the request for specimen withdrawal cannot be processed.

#### 7.1.4.2 Subject Blinding/Unblinding

**NOTE: As of Amendment 06, blinding is no longer applicable as ipilimumab and matching placebo have been removed from the study. Subjects who remain on treatment will receive open-label pembrolizumab monotherapy as per protocol. Text related to ipilimumab/matching placebo and emergency unblinding in this section is no longer applicable.**

STUDY TREATMENT IDENTIFICATION INFORMATION IS TO BE UNMASKED ONLY IF NECESSARY FOR THE WELFARE OF THE PARTICIPANT. EVERY EFFORT SHOULD BE MADE NOT TO UNBLIND THE PARTICIPANT UNLESS NECESSARY.

For emergency situations where the investigator or delegate needs to identify the drug used by a subject and the dosage administered in case of emergency e.g., the occurrence of serious adverse events, he/she will contact the emergency unblinding call center by telephone and make a request for emergency unblinding. As requested by the investigator or delegate the emergency unblinding call center will provide the information to him/her promptly and report unblinding to the Sponsor. Prior to contacting the emergency unblinding call center to request unblinding of a subject's treatment assignment, the investigator or delegate must enter the toxicity grade of the adverse events observed, the relation to study drug, the reason thereof, etc., in the medical chart etc.

For studies that require non-emergency unblinding as part of the study design (eg, disease progression) to support treatment decisions, instructions in this section below should be followed. The emergency unblinding center should not be used for this purpose.

Subjects whose treatment assignment has been unblinded by the investigator/delegate and/or non-study treating physician must be discontinued from study drug, but should continue to be monitored in the trial.

For studies that require unblinding as part of the study design (e.g., disease recurrence, progression, or completion of study treatment) to support treatment decisions, the site must first contact the Sponsor for approval of nonemergent unblinding at the time of central laboratory confirmation of disease recurrence, disease progression, or completion of study treatment. Once authorization is granted by the Sponsor for nonemergent unblinding, the site will contact IVRS/IVXS to receive the participant's unblinded treatment arm. The emergency unblinding center should not be used for nonemergency unblinding.

Treatment/Vaccine identification information is to be unmasked ONLY if necessary for the welfare of the subject. Every effort should be made not to unblind the subject unless necessary.

In the event that unblinding has occurred, the circumstances around the unblinding (e.g., date, reason and person performing the unblinding) must be documented promptly, and the Sponsor Clinical Director notified as soon as possible. Only the principal investigator or delegate and the respective subject's code should be unblinded. Other trial site personnel and Sponsor personnel directly associated with the conduct of the trial should not be unblinded.

#### **7.1.4.3 Calibration of Equipment**

The investigator or qualified designee has the responsibility to ensure that any device or instrument used for a clinical evaluation/test during a clinical study that provides information about inclusion/exclusion criteria and/or safety or efficacy parameters shall be suitably calibrated and/or maintained to ensure that the data obtained is reliable and/or reproducible. Documentation of equipment calibration must be retained as source documentation at the study site.

#### **7.1.5 Visit Requirements**

Visit requirements are outlined in Section 6.0 - Trial Flow Chart. Specific procedure-related details are provided above in Section 7.1 - Trial Procedures.

##### **7.1.5.1 Screening**

Within 30 days prior to treatment randomization, potential subjects will be evaluated to determine that they fulfill the entry requirements as set forth in Section 5.1. Visit requirements are outlined in the Trial Flow Chart (Section 6). Screening procedures may be repeated.

Written consent must be obtained prior to performing any protocol-specific procedure. Results of a test performed prior to the subject signing consent as part of routine clinical management are acceptable in lieu of a screening test if performed within the specified time frame. Screening procedures are to be completed within 30 days prior to the first dose of trial treatment except for the following:

Laboratory tests are to be performed within 10 days prior to the first dose of trial treatment.

- ECOG performance must be assessed within 7 days of the first dose of trial treatment but before randomization.
- For women of reproductive potential, a serum pregnancy test will be performed within 72 hours prior to first dose of trial treatment.

- Tumor imaging must be performed within 30 days prior to the date of randomization.

Subjects may be rescreened after initially failing to meet the inclusion/exclusion criteria. Results from assessments performed during the initial screening period are acceptable in lieu of repeating a screening test if performed within the specified time frame and the results meet the inclusion/exclusion criteria.

#### **7.1.5.2 Treatment Period Visit**

Visit requirements are outlined in Section 6.0 – Trial Flow Chart. Specific procedure-related details are provided above in Section 7.1 – Trial Procedures.

#### **7.1.5.3 End of Treatment Visits**

##### **7.1.5.3.1 Discontinuation Visit**

The Discontinuation Visit should occur at the time study drug is discontinued for any reason. If the Discontinuation Visit occurs 30 days from the last dose of study treatment, at the time of the mandatory Safety Follow-up Visit, procedures do not need to be repeated. Procedures at the time of discontinuation are detailed in Section 6.0 - Trial Flow Chart.

All subjects who discontinue trial treatment for a reason other than disease progression should continue to receive all assessments until PD by RECIST 1.1 or initiation of a new antineoplastic therapy.

Imaging assessments should continue as per the interval stated in the protocol; every 9 weeks for the first 54 weeks and then every 12 weeks thereafter. Additional imaging at the Discontinuation Visit is not required provided that a scan was obtained within 4 weeks prior to the date of discontinuation. In subjects who discontinue trial treatment due to documented disease progression, the scan documenting disease progression is the final required tumor imaging.

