#### **7.1.2.6.2 Tumor Imaging During the Study**

The first on-study imaging assessment should be performed at 9 weeks (63 days  $\pm$ 7 days) from the date of randomization. Subsequent tumor imaging should be performed every 9 weeks (63 days  $\pm$ 7 days) or more frequently if clinically indicated. After 54 weeks (378 days  $\pm$ 7 days), subjects who remain on treatment will have imaging performed every 12 weeks (84 days  $\pm$ 7 days). Imaging timing should follow calendar days and should not be adjusted for delays in cycle starts. Imaging should continue to be performed until disease progression is identified by the investigator and verified by the central imaging vendor (unless the investigator elects to continue treatment and follow iRECIST), the start of new anticancer treatment, withdrawal of consent, or death, whichever occurs first. All supplemental imaging must be submitted to the central imaging vendor.

PR and CR should be confirmed by a repeat imaging assessment. The imaging may be performed, at the earliest, 4 weeks after the first indication of a response, or at the next scheduled scan (i.e., 9 or 12 weeks later), whichever is clinically indicated. Subjects will then return to regular scheduled imaging every 9 or 12 weeks as described above, starting with the next scheduled imaging time point. Subjects who receive additional imaging for confirmation do not need to undergo the next scheduled tumor imaging if it is less than 4 weeks later; tumor imaging may resume at the subsequent scheduled imaging time point.

Per iRECIST (Section 7.1.2.6.6), disease progression should be confirmed by the site 4 to 8 weeks after central verification of site-assessed first radiologic evidence of PD in clinically stable subjects. Subjects who have unconfirmed disease progression may continue on treatment at the discretion of the investigator until progression is confirmed by the site provided they have met the conditions detailed in Section 7.1.2.6.6. Subjects who receive confirmatory imaging do not need to undergo the next scheduled tumor imaging if it is less than 4 weeks later; tumor imaging may resume at the subsequent scheduled imaging time point, if clinically stable. Subjects who have confirmed disease progression by iRECIST, as assessed by the site, will discontinue study treatment. Exceptions are detailed in Section 7.1.2.6.6.

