### **7.1.2.6.3 End of Treatment and Follow-up Tumor Imaging**

In subjects who discontinue study treatment, tumor imaging should be performed at the time of treatment discontinuation ( $\pm 4$  week window). If previous imaging was obtained within 4 weeks prior to the date of discontinuation, then imaging at treatment discontinuation is not mandatory. In subjects who discontinue study treatment due to documented disease progression, and the investigator elects not to implement iRECIST, this is the final required tumor imaging.

In subjects who discontinue study treatment without documented disease progression, every effort should be made to continue monitoring their disease status by tumor imaging using the same imaging schedule used while on treatment (every 9 weeks in Year 1 or every 12 weeks after Year 1) to monitor disease status until the start of a new anticancer treatment, disease progression, death, withdrawal of consent, or the end of the study, whichever occurs first.

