##### **7.1.5.4.1 Follow-up Visits**

All subjects who discontinue initial trial treatment or Second Course Phase trial treatment for a reason other than disease progression should continue to receive all assessments until PD by RECIST 1.1 or initiation of a new antineoplastic therapy.

Subjects who have received the maximum administrations of pembrolizumab indicated above for either initial treatment or Second Course Phase trial treatment, should be followed as indicated in the Follow-up Phase of the study outlined in Section 6.0 - Trial Flow Chart.

Follow-up Visit 1 should be scheduled to coincide with the next scheduled imaging visit to occur at least 9 weeks after the last dose of trial treatment. Assessment for drug-related AEs, including those consistent with immune phenomena, should occur at Follow-up Visit 1. Follow-up Visit 2 should be scheduled to coincide with the next scheduled imaging visit to occur at least 18 weeks after the last dose of trial treatment. After Follow-up Visit 2, subjects only need to be assessed every 9 weeks ( $63 \pm 7$  days) or 12 weeks ( $84 \pm 7$  days) as defined in Section 7.1.2.6 – Tumor Imaging and Assessments of Disease, by radiologic imaging to monitor disease status, development of drug-related SAEs and ECIs, and initiation of new antineoplastic therapy. Unless otherwise noted in Section 6.0 - Trial Flow Chart, every effort should be made to collect subject information on the start of new antineoplastic therapy, disease progression, and/or death.

Subjects who are eligible to receive retreatment according to the criteria in Section 7.1.5.6 – Second Course Phase will move to the Second Course Phase when they experience disease progression.

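### Do the uneven imaging-stop rules let sites end scans before BICR verifies progression, and so bias PFS?

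*Combined protocol and SAP*

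**What the plan says.** Three first-course passages end imaging at progression without naming the assessor:

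- Section 7.1.5.3.1: "In subjects who discontinue trial treatment due to documented disease progression, the scan documenting disease progression is the final required tumor imaging".
- Section 7.1.2.6.3, for the same subjects: "and the investigator elects not to implement iRECIST, this is the final required tumor imaging".
- Section 7.1.5.4.1, for subjects who stop for another reason: they "should continue to receive all assessments until PD by RECIST 1.1 or initiation of a new antineoplastic therapy".

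Section 7.1.2.6.6 adds that a clinically unstable subject "should be discontinued from study treatment at site-assessed first radiologic evidence of PD, and is not required to have repeat tumor imaging". That sentence goes on to limit the waiver to confirmation of progression under iRECIST.

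Other passages tie the end of imaging or of disease follow-up to BICR:

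- Section 7.1.2.6.2: "Imaging should continue to be performed until disease progression is identified by the investigator and verified by the central imaging vendor". Exceptions are continued treatment under iRECIST, new anticancer treatment, withdrawal and death.
- The note under Table 8, where BICR has not verified progression: "imaging should be collected and submitted to the central imaging vendor with verification of progression (VOP) request until RECIST 1.1 PD is verified by BICR".
- Section 1.0 (Duration of Participation) and footnote b of the Section 6.1 flow chart also use BICR-verified progression as the end point.

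Section 7.1.2.6.5 makes BICR under RECIST 1.1 the default for the date of progression and for guidelines that depend on disease status. Under Table 11, a subject with neither BICR progression nor death is censored in the primary PFS analysis at the last disease assessment, or at the last one before new therapy.

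**The concern.** A site that reads Section 7.1.5.3.1 or 7.1.2.6.3 alone could take its own scan reading as the documented progression and stop imaging. If BICR did not agree on that scan, the subject would have no PFS event and would be censored there. As Table 11 is written, a death after two or more consecutive missed assessments would not restore the event in the primary analysis. Such subjects are likely to be close to a BICR event, so the censoring would be informative. Section 8.7.2 sets no PFS event count for either look, so lost events would not be made up by waiting. Two things would be at stake for a primary endpoint: power, and the hazard ratio if early stopping differed between arms.

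**Working it through.** **1. Do the passages conflict once read together?** No first-course passage says that imaging ends at site-assessed progression; three leave the assessor open. Section 7.1.2.6.5 supplies BICR as the default. Section 5.8.1 lists BICR-verified progression as the reason for stopping treatment, and Section 2.1 asks for submission to BICR before treatment is stopped. A subject who stops because of documented progression will therefore usually have BICR-verified progression. The exception is the clinically unstable subject who stops at the site's reading. The Table 8 note covers that case expressly: "Whether or not treatment continues, imaging should be collected and submitted to the central imaging vendor". A site following the whole protocol already does what a rewording would ask.

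**2. Reproducing the plan's power.** Inputs from Section 8.9 and Table 15: 389 events, HR 0.69, one-sided alpha 0.006, 1:1 allocation, first look at 357 events.

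- Fixed design: power = Φ(−ln(0.69)·√389/2 − 2.512) = Φ(3.659 − 2.512) = 0.874.
- Two looks with Lan-DeMets O'Brien-Fleming spending: bounds 2.6415 and 2.5865, total power 0.868. Table 15 gives 2.6394, 2.5869 and 0.8692.

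The plan's figure reproduces.

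**3. Power if events were lost.** The documents give no rate of site progression that BICR fails to verify. One illustration assumes that 75% of the 357 events are progressions (0.75 × 357 = 268) and that 10% to 20% of site progressions are unverified, which puts 27 to 54 events at risk (27/357 = 8%, 54/357 = 15%). Under assumed losses, two-look power is:

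| Share of events lost | Events at the two looks | Power |
|---|---|---|
| 0% | 357 / 389 | 0.868 |
| 5% | 339 / 370 | 0.848 |
| 10% | 321 / 350 | 0.824 |
| 15% | 303 / 331 | 0.798 |
| 20% | 286 / 311 | 0.768 |

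The 8% to 15% range overstates the likely loss, even at the assumed rates:

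- It applies a rate for unverified site readings to events that BICR has, by definition, already counted.
- It treats every unverified reading as a lost event. Clinically stable subjects may stay on treatment and are rescanned at 4 to 8 weeks, with the images sent to the central vendor.
- Death after at most one missed assessment, before new therapy, still counts as an event.
- New anticancer therapy ends imaging even under Section 7.1.2.6.2, so clearer wording would not recover those subjects.

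**4. Hazard ratio.** The simulation used the plan's control PFS (medians 6.5 months, then 14.5 months), HR 0.69, 20-month accrual, cutoff at month 39, 13% yearly dropout and the 9-week then 12-week scan schedule, with 40,000 subjects per arm. A share q of subjects stops imaging one scan before BICR would find progression, and no lost event is recovered through death. Monte Carlo error on the HR is about 0.006. The reference value is 0.706 rather than 0.69 because of ties at scan dates and Monte Carlo error.

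| q control / experimental | HR | Events per 568 |
|---|---|---|
| 0 / 0 | 0.706 | 382 |
| 5% / 5% | 0.707 | 368 |
| 10% / 10% | 0.701 | 353 |
| 20% / 20% | 0.708 | 324 |
| 10% / 5% | 0.733 | 360 |
| 5% / 10% | 0.685 | 363 |
| 20% / 10% | 0.766 | 339 |
| 10% / 20% | 0.660 | 340 |

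With a true HR of 1, the reference is 1.013; 10% / 20% gives 0.929 and 20% / 10% gives 1.069. Equal stopping costs events but hardly moves the HR. Unequal stopping moves it in either direction.

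**5. What could still change?** Sections 8.0 and 8.7.2 state that the first interim analysis is done and that the second interim and final analyses will not be performed. PFS did not meet its success criteria. The futility rule that was brought forward is described in Section 8.7.2 as based on OS, which does not depend on scans.

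**The case for a change.** The ambiguity is more than a matter of style. Section 7.1.2.6.3 makes its stop rule depend on the investigator's choice about iRECIST, and Section 7.1.2.6 places that choice after the investigator's own finding of progression. That invites the site-reading interpretation. In the body of Table 8, the clinically unstable column says that no more imaging is needed after a repeat scan, whatever that scan shows; only the note beneath mentions BICR. Blinding makes a difference between arms less likely but cannot exclude it, because toxicity or clinical instability could differ by arm.

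Sensitivity analysis 2 counts treatment discontinuation for reasons other than complete response, or new therapy, as progression, so it probes this scenario. Yet the sensitivity set is not described cleanly. The text of Section 8.6.1.2 gives censoring after missed assessments to sensitivity analysis 1, while Table 11 gives it to the primary analysis.

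What stands: some sites may have stopped scanning early, and the completed PFS analysis cannot be assumed free of it. What does not stand is the claim that the plan directs them to stop. The unstable-subject waiver concerns iRECIST confirmation only, and the Table 8 note is explicit.

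Nor is a simple substitution of wording harmless. Section 7.1.5.4.1 also governs the Second Course. Its images need not go to the central vendor (Section 7.1.2.6.4), and its survival follow-up starts after local site-assessed progression (Section 6.2, footnote b). Requiring BICR verification there would create a conflict that does not exist now.

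**Conclusion.** This is a clerical unevenness: three passages leave the assessor unnamed, and the Table 8 note, Section 7.1.2.6.2 and the BICR default in Section 7.1.2.6.5 fill the gap. No figure in the plan is wrong; the PFS power reproduces at 0.868 against 0.8692. The possible cost rests wholly on assumed rates. At a 10% loss of events, power would be 0.824. The HR would stay within 0.701 to 0.708 if stopping were equal across arms and would range from 0.660 to 0.766 over the unequal rates tried. The documents give no evidence of unequal stopping, and treatment was double-blind until Amendment 06. With no PFS analysis left to run, rewording would change neither a result nor a conclusion. The point remains only as a modest caveat when reading PFS from the first interim analysis.
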